1. HNSCC

- i. Inoperable/incurable locally advanced or recurrent/metastatic HNSCC with no previous radiotherapy treatment
- ii. Inoperable/incurable locally advanced or recurrent/metastatic HNSCC with previous radiotherapy treatment (re-irradiation)

2. cSCC in the head and neck region

- i) Inoperable/incurable locally advanced or recurrent/metastatic cSCC with no previous radiotherapy treatment
- ii) Inoperable/incurable locally advanced or recurrent/metastatic cSCC with previous radiotherapy treatment (re-irradiation)

3. LRBC

- i) Locally recurrent breast cancer with previous radiotherapy treatment (re-irradiation)

- **Primary objective:**

1. To assess the real-world implementation of superficial hyperthermia [using CE marked water-filtered infrared A (wIRA) machine] in addition to palliative SOC radiotherapy

- **Secondary objectives:**

1. To assess the best objective response rate (ORR) of the lesions treated with the combination of superficial hyperthermia (wIRA) and palliative radiotherapy
2. To determine the tolerability and safety profile of the combination treatment of superficial hyperthermia (wIRA) and palliative radiotherapy
3. To evaluate the median progression-free survival (PFS) and overall survival (OS) of patients
4. To assess the median duration of objective response and locoregional control rates at 6 and 12 months
5. To assess patient-reported outcome measures (PROMs) and quality of life (QoL) of patients using the European Organization for Research and Treatment of Cancer (EORTC) Quality of Life Core Questionnaire (QLQ-C30) and head and neck module (QLQ-H&N35)
6. To assess the differences in the efficacy between the lesion(s) treated with radiotherapy with hyperthermia with the lesion(s) treated with radiotherapy alone in those patients with at least 1 additional lesion that is not suitable for treatment with hyperthermia
7. To compare clinical outcome of patients treated with combination of superficial hyperthermia and radiotherapy who may or may not undergo subsequent immunotherapy with the retrospective data of historical cohorts

- **Exploratory objectives/translational research:**

Collection of samples such as archival tumour sample, fresh tumour biopsy/resected sample when available, blood (PBMC), and saliva, for translational research (see below).

- **Table 1: Objectives and endpoints**

	Objectives	Endpoints
--	-------------------	------------------

Primary	To assess the real-world implementation of superficial hyperthermia using CE marked water-filtered infrared A (wIRA) in addition to palliative SOC radiotherapy as part of their standard of care (SOC)	
1. Quantitative: the total number and types of cancer patients successfully treated with the combination of superficial hyperthermia and palliative radiotherapy.
 
2. Descriptive: to evaluate the real-world implementation by the NASSS (non-adoption, abandonment, and challenges to scale-up, spread, and sustainability) framework using NASSS-CAT (complexity assessment tool) ⁵

Secondary	
1. To assess the best objective response rate (ORR) of the lesion(s) treated with (1) combination of superficial hyperthermia with palliative radiotherapy; (2) radiotherapy alone
 
2. To determine the tolerability and safety profile of superficial hyperthermia in patients receiving SOC palliative radiotherapy
 
3. To evaluate the median local and global progression-free survival (PFS) and median overall survival (OS) of patients at 12 months after the last patient is recruited
 
Local: refer to the lesions treated by radiotherapy +/- superficial hyperthermia.
 
Global: local and distant (non-treated lesions)
 
4. To assess the median duration of objective response and locoregional control rates of the treated lesion(s) at 6 and 12 months
	
1. Best ORR: Defined as the proportion of patients achieving either a Complete Response (CR) or a Partial Response (PR).
 
Complete Response (CR): Disappearance of all target lesions.
 
Partial Response (PR): ≥ 30% decrease in the sum of diameters of target lesions, taking as reference the baseline sum diameters.
 
2. Local adverse events (AEs) and adverse reactions (ARs) will be assessed by Common Terminology Criteria for Adverse Events (CTCAE) version 5.0.
 
3. PFS: Defined as the time from baseline to the first documented progressive disease (PD) or death from any cause, whichever occurs first.
 
PD: At least a 20% increase in the sum of diameters of target lesions or development of new lesions, with the date of progression recorded by a clinician in the patient's hospital records.
 
OS: The time from the start of treatment to death from any cause.
 
Patients not experiencing an event (progression or death) will be censored at the time of the final analysis at the date last known to be alive and progression-free.
 
4. Duration of Objective Response: Defined as the time from the first documented Complete Response (CR) or Partial Response (PR) to disease progression or metastasis.

		Locoregional Control Rate: The proportion of patients whose primary tumour site remains free from progression.
	5. To assess patient-reported outcomes measures (PROMs)	
5. PROMs assessment using the European Organization for Research and Treatment of Cancer (EORTC) Quality of Life Core Questionnaire (QLQ-C30), European Organisation for Research and Treatment of Cancer Quality of Life Questionnaire Head and Neck Module (QLQ-H&N43) (for HNSCC cohort)
 
PROMs will be collected at baseline, during treatment (after the 3rd fraction of radiotherapy), 6 weeks post-treatment, 12-weeks post-treatment.

	6. To assess the differences in the efficacy between the lesion(s) treated with radiotherapy with hyperthermia with the lesion(s) treated with radiotherapy alone in those patients with at least 1 additional lesion that is not suitable for treatment with hyperthermia	6. Percentage of best ORR, duration of response and disease control rates at 6 and 12 months in the lesion(s) treated with hyperthermia and radiotherapy versus lesion(s) treated with radiotherapy alone.
	7. To compare clinical outcome of patients treated with superficial hyperthermia in addition to SOC radiotherapy with historical control	7. Retrospectively collect data for historical cohort of similar cancer patients treated with SOC radiotherapy alone

⁵Descriptive primary endpoint: evaluation of the real-world implementation by the NASSS-CAT

Introduction of the new technology into the NHS can be very complex and the process of which cannot be easily captured by the traditional clinical trial endpoints. To this end, the non-adoption, abandonment, scale-up, spread, and sustainability (NASSS) framework allows the description of the complexity in real-world implementation of new technology consisting of six domains including (a) the condition or illness, (b) the technology, (c) the value proposition, (d) the adopter system, (e) the health care organization(s), and (f) the wider system (especially regulatory, legal, and policy issues). The seventh domain is cross-cutting, considering how all these domains interact and emerge over time (27). Extending the NASSS framework and building on a complexity assessment tool (CAT), four NASSS-

CAT tools were previously developed to apply the complexity principles to evaluate the introduction of technology in healthcare setting (28). These includes NASSS-CAT SHORT, NASSS-CAT LONG, NASSS-CAT PROJECT and NASSS-CAT INTERVIEW (see appendix). We will use these tools to evaluate the descriptive part of the primary endpoint of this study.

7. Study design & Flowchart

○ Study design

This is a prospective study to assess the real-world implementation of superficial hyperthermia (wIRA) in combination with SOC palliative radiotherapy in cancer patients not suitable for radical treatment and have superficial lesion(s) suitable for wIRA treatment. All eligible patients will be recruited in the study by the clinical team following discussion with the chief investigator or the designated clinical sub-investigator. Patients will be consented for palliative radiotherapy as per standard treatment. The radiotherapy dose delivered will be clinician's choice based on SOC table 1 schedules.

Table 2: Schedule of radiotherapy and hyperthermia

Palliative radiotherapy (Primary vs Re-irradiation)	Dose	Fractions	Radiotherapy	Hyperthermia
Primary or Re-irradiation (previous standard palliative dose)*^	27Gy	6	Twice per week	Once per week
Re-irradiation (previous radical dose)*^	20Gy	5	Once a week (up to 5 weeks)	Once per week
Primary or Re-irradiation (previous standard palliative dose)*^	20Gy	5	Daily over 1 week	Twice per week
Re-irradiation (previous radical or palliative dose)*^	20Gy	10	Daily over two weeks	Twice per week
Primary or Re-irradiation (previous standard palliative dose)*^	36Gy	6	Once a week	Once per week

*The combined dose from previous RT and proposed RT fractionation will not exceed tolerance dose for critical organs (assuming recovery if necessary, as per routine clinical practice). If completing the full radiotherapy schedule would result in exceeding the tolerance dose to critical organs, treatment may be administered on a weekly basis until the tolerance threshold is reached.

[^]The combined dose from previous RT and proposed RT fractionation will not exceed tolerance dose for critical organs (assuming recovery if necessary, as per routine clinical practice) and the combined dose to soft tissue of the irradiated area will not exceed 70Gy in equivalent 2Gy per fraction (without assuming recovery).

The patients will receive hyperthermia either once a week or twice a week (as listed in Table 1) using hydrosun® TWH1500 with palliative radiotherapy. The patients will receive hyperthermia treatment for 1 hour before going for palliative radiotherapy as per standard of care. For patients who will undergo 27Gy/6#, they will receive hyperthermia once a week for three weeks during the course of palliative radiotherapy. For patients undergoing 20Gy/5# over five weeks or 36Gy/6# over six weeks, they will receive hyperthermia once a week. For patients undergoing 20Gy/5# over one week or 20Gy/10# over two weeks, they will receive hyperthermia two times per week during their treatment.

Most of the HNSCC patients will be suitable for palliative pembrolizumab (if the tumours are CPS \geq 1) and the cSCC patients will be suitable for cemiplimab if they have an ECOG performance status \leq 1. We would aim to start palliative pembrolizumab within 6 weeks (+/- 2 weeks) of completing palliative radiotherapy if patients are deemed to be suitable and fit for this treatment as part of the standard of care. LRBC patients will undergo systemic treatments as per standard of care according to their previous treatment histories and breast cancer subtypes.

Patients will be assessed during their treatment for toxicities, and rate of adverse events will be assessed by CTCAE version 5.0. Follow-ups and assessment of response will be done as per standard of care.

When appropriate, we will aim to collect biological samples from each patient for translational research (see below) including archival tumour sample, fresh tumour biopsy or resection sample when available, blood samples at different time intervals before, during and after their treatments as well as saliva and mouth swab at the same time points when appropriate. The samples will be analysed to further assess the tumour microenvironment, the peripheral immune response and to identify predictors of treatment response.

For all patients, blood samples will be collected at baseline (at time of consent), before the first round of hyperthermia/radiotherapy treatment*, after the first round of hyperthermia/radiotherapy

treatment**, 6 weeks (+/- 2 weeks)*** post hyperthermia/radiotherapy, 12 weeks (+/- 2 weeks)*** post hyperthermia/radiotherapy, and at the first disease progression post hyperthermia/radiotherapy. Additionally, for those patients who will subsequently undergo anti-PD1/PD-L1 checkpoint inhibitor therapy (immunotherapy) as part of the standard of care, we will collect blood samples at immunotherapy baseline, 3 weeks (+/- 2 weeks) post-immunotherapy baseline, 6 weeks (+/- 2 weeks) post-immunotherapy baseline and at the first disease progression post-immunotherapy baseline. Other samples for translational research will be collected on clinician's discretion and up to a total of six times. As a standard of care, we routinely collect patient reported outcomes to assess toxicity to radiotherapy treatment thus we will continue to collect for this study.

* May be omitted if baseline bloods have been obtained. Omission would occur due to logistical issues (i.e., difficult to arrange with the participant).

** This could usually be done after 3rd fraction of radiotherapy (if not possible, aim for 4th fraction of RT).

*** This allows for flexibility; due to the nature of the study, it may be that logistically issues make it difficult to arrange precisely at the exact timepoint.

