Patient cohorts	
1) HNSCC
 
 i) Inoperable/incurable or recurrent/metastatic HNSCC with no previous radiotherapy treatment ii) Inoperable/incurable or recurrent/metastatic HNSCC with previous radiotherapy treatment (re-irradiation) 
2) cSCC
 
 i) Inoperable/incurable or recurrent/metastatic cSCC with no previous radiotherapy treatment ii) Inoperable/incurable or recurrent/metastatic cSCC with previous radiotherapy treatment (re-irradiation) 
3) LRBC
 
locally recurrent breast cancer with previous radiotherapy treatment (re-irradiation)
	

Study Type	Interventional study to implement superficial hyperthermia using wIRA machine in the real-world setting
Study endpoints	The end of the study definition is 12 months from the last participant recruited into the study after the 24-month recruitment period.
Main Inclusion Criteria	
 1. Patient with histologically confirmed incurable or inoperable cancers with disease [at least one superficial lesion(s) or lymph node(s)] suitable for hydrosun® TWH1500 treatment 2. Patient undergoing standard of care palliative radiotherapy (suitable with the pre-specified dose and fractionation in the protocol) 3. Aged ≥18 years old 4. Eastern Cooperative Oncology Group (ECOG) performance status 0 to 2 5. Patient with capacity to consent
Statistical Methodology and Analysis	This is a prospective study aiming to implement superficial hyperthermia using wIRA machine in the real-world setting and to recruit 15-20 patients in each disease cohort above (total = up to 60), which is the realistic target for two years.
Human Tissue and blood Samples (if applicable)	Peripheral bloods will be collected, and archival tissues will be requested to assess the peripheral and tissue immune markers. Other biological samples such as saliva, oral swab, urine, and stool samples may be collected for future translational research.
Data collected/storage (if applicable)	Patients' demographics, smoking and alcohol history, tumour characteristics, treatment details and responses, recurrences and survivals will be obtained from clinical record and recorded on paper Case Report Forms (CRFs).

5 Introduction

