5.1 Schedule of events

	Screening (Visit 0)	Baseline (Visit 1)	Pre-HT (Visit 2)	Post-HT/RT (Visit 3)	6 weeks post HT/RT (Visit 4)	12 weeks post HT/RT (Visit 5)	Disease progression (Visit 6)	10 baseline (Visit 7)	10 – 3wks (Visit 8)	10-6wks (Visit 9)	10-disease progression (Visit 10)	12 months post HT/RT
Eligibility criteria	X											
Participant information	X											
Informed consent		X										
Medical record monitoring		X	X	X	X	X	X	X	X	X	X	X
EORTC QLQ-C30		X		X	X	X						
EORTC QLQ H&N35		X		X	X	X						
Sample collection: blood		X	X*	X	X	X	X	X	X	X	X	
Sample collection: saliva		X	X*	X	X	X	X	X	X	X	X	

*This may be omitted if baseline measures were collected. Omission may occur due to logistical issues (i.e., difficult to arrange with the participant)

Abbreviations: HT, hyperthermia; IO, Immunotherapy; RT, radiotherapy.

- **Treatment visits**

This is an interventional study to implement superficial hyperthermia in the real-world setting, and the patients will continue their clinical visits and follow-up as per normal standard of care. We will obtain the treatment outcome from medical records of patients. It will be during patients' SOC visits that we will collect biological samples and assess PROMs. All patients will be assessed using the European Organization for Research and Treatment of Cancer (EORTC) Quality of Life Core Questionnaire (QLQ-C30). Additionally, the HNSCC cohort will also be assessed using the European Organisation for Research and Treatment of Cancer Quality of Life Questionnaire Head and Neck Module. PROM assessments will take place during the same timepoints as biological sample collection, with the last PROM assessment taking place at 12 weeks post radiotherapy.

8. Subject selection

We will have the following cohorts of patients undergoing standard of care treatments, which we plan to include 15 to 20 patients in each disease cohort* and up to 60 patients in total:

1. HNSCC cohorts

- i. Inoperable/recurrent HNSCC with no previous radiotherapy treatment
- ii. Inoperable/recurrent HNSCC with previous radiotherapy treatment (re-irradiation)

2. cSCC cohort

- i. Inoperable/recurrent cSCC with no previous radiotherapy treatment
- ii. Inoperable/recurrent cSCC with previous radiotherapy treatment (re-irradiation)

3. LRBC cohorts

- i. Inoperable locally recurrent breast cancer with previous radiotherapy treatment (re-irradiation)

* The number of participants may vary between each group

- **Subject inclusion criteria**

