The patient recruitment for the prospective study will initially be 24 months from the commencement of the study at coordinating site, Guy's and St. Thomas' NHS Foundation trust. Thereafter, the patients will be followed up for their long-term treatment outcome and survival as per normal standard of care. We will continue to obtain relevant information on patients' treatment and survival outcome from patients' medical records. The end of the study definition is 12 months from the last participant recruited into the study. We will assess whether the endpoints and outcomes are met at the end of the study, particularly the real-world implementation of superficial hyperthermia (using CE marked water-filtered infrared A (wIRA) machine) in addition to palliative radiotherapy and whether we are able to recruit the target number of patients.

We will submit the protocol for a major amendment towards the end of the study if the study is to continue for up to an additional 3 years of recruitment, providing further funding is obtained. Otherwise, we will analyse all data and produce the final study report at the end of third year.

The criteria for progression beyond the two-year recruitment period are set as below:

1. The study recruits well and reaches the target number of patients (up to 60 patients)
2. The study showed that superficial hyperthermia with wIRA could be implemented in the real-world setting and used in combination with palliative radiotherapy in cancer patients
3. Further funding is obtained to continue beyond the two-year recruitment period

10. Laboratories

Collected patients' samples from Guy's Hospital as part of translational research will be transferred to [name] laboratory at Kings College London for further processing. The samples will be pseudo-anonymised with sample IDs which can be linked to patients. The sample processing will be done by the research assistant appointed for the study and/or [name] lab members and only those with KHP passport will have access to patients' confidential information. The samples will not be transferred or given to anyone without an MTA agreement. However, if there are any successfully generated organoids from any fresh samples, the anonymised organoids may be shared with collaborators. Based on the consent from patients, any other unused blood, saliva, oral swab, urine, and stool samples will be stored at Guy's and St Thomas' head and neck biobank beyond the ethics approval date of the project.

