In line with the study sponsor conditions and HRA guidance, if a SAE is discovered and thought to be related to superficial hyperthermia (+/- SOC palliative radiotherapy), the CI will immediately report upon knowledge of the event to the R&D Department within 24 hours. If the SAE is considered to be related to superficial hyperthermia (+/- SOC palliative radiotherapy) and unexpected, it will also be reported to the relevant REC committee within 15 days of the CI becoming aware of the event. The HRA defines SAEs as related to the study if it involves the administration of any of the research procedures and unexpected as in that it was not listed in the protocol as an expected occurrence. If the CI deems a SAE to be disease-related and not related to the superficial hyperthermia (+/- SOC palliative radiotherapy), the SAE will be documented but only reported in the final study report. Therefore, only SAEs that are localised to the site of hyperthermia (local adverse events) will be reported. Participants will be monitored for SAEs for 6 weeks after completion of radiotherapy. All documentation relating to SAEs will be kept in the Trial Master File.

12. Compliance and withdrawal

- **Subject compliance**

We will monitor the percentage of approached participants who consent to taking part in the study during the first year of recruitment.

- **Withdrawal/dropout of subjects**

We will monitor the percentage of participants who withdraw consent or drop out from the study after taking part. We will replace the subjects if necessary to make up the total target number of patients (n=30) as long as this is within the recruitment period.

- **Protocol compliance**

The patients will undergo routine treatments as per standard of care.

13. Data

- **Data management**

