This is a prospective study to assess the implementation of wIRA superficial hyperthermia machine in the real-world setting and no formal power calculation is performed. The number of patients chosen for each cohort is the expected number of patients that we anticipate recruiting within 24 months based on the number of cancer patients that we treat at Guy's Cancer Centre. The study will initially commence as a single-site study at GSTT. Other UK sites may be added via a substantial amendment in due course if they acquire the same CE marked machine and would like to participate in the study. Consideration as to whether sites outside of the UK will be able to take part in the study will be considered in due course although this may not be possible due to the different health policy and the additional ethical approval requirement. The data from this prospective study will be used to calculate the sample size required if we extend the study beyond two years of recruitment or to plan a future interventional study, which will be submitted as a major amendment.

15. Ethical considerations

- **Research Ethics Committee (REC) review & reports**

Before the start of the trial, approval will be sought from an NHS REC for the trial protocol, informed consent forms, patient information sheet, and GP information letters.

Any amendments to the protocol or study documents will be reviewed by the Sponsor, sent to the REC for review and approvals. No changes will be implemented until approval has been received from the REC and approved by the Trust R&D department, if required.

All correspondence with the REC will be retained in the Trial Master File.

An annual progress report (APR) will be submitted to the REC within 30 days of the anniversary date on which the favourable opinion was given, and annually until the trial is declared ended. The Chief Investigator's will approve the annual report which will be submitted by the CI or delegate.

The CI will notify the REC of the end of the trial within 90 days of the end of the study. If the trial is ended prematurely, the CI will notify the REC, including the reasons for the premature termination.

Within one year after the end of the trial, the Chief Investigator will submit a final report with the results, including any publications/abstracts, to the REC.

- **Peer review**

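### The quantitative primary endpoint counts successfully treated patients without a denominator, so with dropouts replaceable it cannot give the delivery rate among enrolled patients, and progression criterion 2 is tied to no delivery measure

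*Protocol*

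**What the plan says.** The Synopsis and Table 1 (section 6) give the primary objective two endpoints. The quantitative one is "the total number and types of cancer patients successfully treated with the combination of superficial hyperthermia and palliative radiotherapy". The descriptive one is an evaluation with the NASSS-CAT tools. The protocol does not say what makes a patient successfully treated, out of how many patients the total is counted, or what total would be enough.

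Five other places bear on the count:

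- **Replacement.** Section 12 (Withdrawal/dropout of subjects) says "We will replace the subjects if necessary to make up the total target number of patients (n=30"), limited to the recruitment period. The same section monitors the percentage who withdraw or drop out and, in the first year, the percentage of approached patients who consent.
- **Target.** The Synopsis aims to "recruit 15-20 patients in each disease cohort above (total = up to 60"). Section 8 adds that "The number of participants may vary between each group". Section 14 says that "no formal power calculation is performed" and gives the basis of the target: "The number of patients chosen for each cohort is the expected number of patients that we anticipate recruiting within 24 months".
- **Shortened courses.** Under Table 2 (section 7), footnote * says that, where the full radiotherapy schedule would exceed organ tolerance, "treatment may be administered on a weekly basis until the tolerance threshold is reached".
- **Progression.** In section 9 (End of Study Definition), criterion 1 concerns recruitment and criterion 3 funding. Criterion 2 asks whether the study showed that wIRA hyperthermia "could be implemented in the real-world setting and used in combination with palliative radiotherapy". It names no rate, count or threshold.
- **Records.** Section 13 keeps screening and enrolment logs and records treatment details on case report forms.

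**The concern.** The study asks whether the technology can be delivered alongside palliative radiotherapy in routine care. A reader will want to know how many of the patients who agreed to the combination actually received it. A bare total does not answer that. Replacing dropouts weakens it further, because a patient who leaves and is replaced no longer shows in the total.

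The missing definition of success adds a second gap. Planned courses differ in length, and some may be shortened within the protocol, yet nothing says how a shortened or incomplete course is classified. The classification could then be settled after the data are known, in an open single-arm study whose result feeds a decision on up to three more years of recruitment (section 9) and the sample size of later work (section 14). The same table defines the secondary endpoints more closely: objective response, for example, is a proportion with explicit response criteria.

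**Working it through.** **1. The plan's own target.** Three disease cohorts of 15 to 20 give 3 × 15 = 45 and 3 × 20 = 60, so a total of up to 60 follows from its inputs. The target is an accrual estimate, and there is no power calculation to reproduce. The replacement target of 30 in section 12 follows from no stated input and conflicts with up to 60 in the Synopsis, section 8 and section 9.

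**2. What replacement does to the count.** The protocol gives no completion rate, so completion from 100% to 50% is an assumed range. If dropouts are replaced until the target count is reached, enrolled = target ÷ completion rate, rounded up. Intervals are exact (Clopper-Pearson) 95%.

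| Count reported | Enrolled | Delivery rate | 95% CI |
|---|---|---|---|
| 30 | 30 | 100% | 88.4 to 100% |
| 30 | 34 | 88.2% | 72.5 to 96.7% |
| 30 | 40 | 75.0% | 58.8 to 87.3% |
| 30 | 45 | 66.7% | 51.0 to 80.0% |
| 30 | 60 | 50.0% | 36.8 to 63.2% |

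The endpoint as written reports 30 in every row.

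**3. How far replacement can go depends on the unresolved target.** Replacement stops when recruitment closes, and section 14 expects accrual of up to 60 in that time. With a target of 30, up to 60 − 30 = 30 patients could be replaced within that accrual. With a target of 60, the expected accrual leaves 60 − 60 = 0 to spare, and unreplaced dropouts would lower the total.

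**4. What the undefined word could do.** Hyperthermia sessions planned under Table 2 and the text below it:

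- 27 Gy in 6, twice weekly: 3 weeks × 1 = 3
- 20 Gy in 5, weekly: 5 × 1 = 5
- 20 Gy in 5, daily over one week: 1 × 2 = 2
- 20 Gy in 10, over two weeks: 2 × 2 = 4
- 36 Gy in 6, weekly: 6 × 1 = 6

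Assume each planned session is delivered independently with probability p. The protocol gives no p. Then P(all k sessions) = p^k and P(at least one) = 1 − (1 − p)^k.

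| p (assumed) | All sessions, k = 2 | All sessions, k = 6 | At least one, k = 2 |
|---|---|---|---|
| 0.80 | 64% | 26% | 96% |
| 0.90 | 81% | 53% | 99% |
| 0.95 | 90% | 74% | 99.8% |

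At p = 0.90, 60 patients would yield about 60 successes if one session sufficed. If all sessions were needed, they would yield about 49 (everyone on the two-session schedule) to 32 (everyone on the six-session schedule). A real mix of schedules would fall between those two figures.

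**5. What a fixed denominator would show.** With 60 patients, 54 successes are 90% (79.5 to 96.2%), 45 are 75% (62.1 to 85.3%) and 30 are 50% (36.8 to 63.2%). These are distinguishable results that a reader can judge.

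**The case against.** The strongest reply is that the design can reveal failure in other ways, and much of it stands.

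- **Replacement is bounded.** It ends with recruitment, and the sample size is what the centre expects to accrue in that period. A low total would be visible, and criterion 1 looks at recruitment. A reader might infer that failures never reduce the count, or that the endpoint cannot show implementation failure. The protocol supports neither.
- **There is a second primary endpoint.** The NASSS-CAT tools deal with adoption, abandonment and organisational barriers. The protocol chose them because ordinary trial endpoints capture these poorly. They have no decision rule, but they can describe failure.
- **Partial courses are not said to count.** Section 7 states the sessions patients will receive on each schedule, so a full planned course is an equally natural reading. Footnote * describes a permitted adaptation of radiotherapy, which is not failed delivery of hyperthermia.
- **Criterion 2 is not tied to the count alone.** A literal reader might say that one treated patient satisfies it. Section 9 refers to the endpoints and outcomes generally, and extension also needs recruitment, funding and an amendment.
- **The denominator can be recovered** from the logs and the monitored percentages, and the choice of interval may be left to a statistical analysis plan.

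This narrows the point without removing it. The monitored percentages enter neither the endpoint nor criterion 2, and the numerator and denominator of a primary endpoint belong in the protocol. The absence of a power calculation is acceptable here and is not part of the criticism.

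**Conclusion.** The concern holds in a limited form. The count alone cannot give the delivery rate among enrolled patients, because it has no denominator, success is undefined and dropouts may be replaced during recruitment. Criterion 2 is linked to no delivery measure. It would go too far to conclude that the study is unable to show poor implementation, or that shortened courses will be counted as successes.

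On size, one reported count of 30 fits delivery rates from 100% down to 50% if up to 60 patients are enrolled. The 30 of 45 example and the per-session probabilities are illustrative assumptions, as is independence between sessions; none is an estimate for this study. Replacement also applies only to patients who withdraw or drop out. Someone who stays in the study but misses sessions is affected by the missing definition and not by replacement.

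The conflict between 30 and up to 60 is a definite inconsistency, and it matters here because it determines how many dropouts could be replaced.

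**What to change.** 1. Keep the count by cancer type. Add, as the primary quantitative summary, the proportion with exact 95% CI of patients who received all hyperthermia sessions and radiotherapy planned for them.
2. Report courses shortened under footnote * as one separate category and other partial courses as another, so that permitted adaptations are not classed as delivery failures.
3. Use all consented patients, including those later replaced, as the denominator. Report the same proportion among patients who started treatment, so that deterioration before treatment can be seen apart from problems of delivery.
4. State before any data review that criterion 2 will be judged on this proportion together with the NASSS-CAT findings.
5. Reconcile the replacement target of 30 in section 12 with the total of up to 60 in the Synopsis, section 8 and section 9.

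The change is one of wording. The treatment records, enrolment logs and dropout monitoring it needs are already planned in sections 12 and 13. The price is a headline figure that may look less favourable than a total.
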